3.10.5. Systemic Reaction

Among systemic AEs / SAEs associated with study interventions that will be solicited and documented are as follows:

- Fever
- Irritability
- Tiredness
- Anorexia
- Vomiting
- Tachycardia
- Seizure
- Hypotension

Similar safety protocol will be adhered to as in 3.10.4 with adjustments made for systemic reactions.

3.10.6 Reporting of AEs / SAEs to the Institution Review Board (IRB)

All AEs will be recorded in the CRFs. AEs of grade 3 and above will be reported to the UKM Human Ethics Committee within 5 business days. All SAEs (including Serious Unexpected Suspected Adverse Events (SUSARs)) will be reported within 24 hours of occurrence (expedited reporting), to the UKM Human Ethics Committee. The reporting procedures for SAEs should adhere to the following steps:

- i) The SAEs initial report form should be filled in by the assessors (medical officers) and reviewed and signed by the PI ([name] [name]) or the co-investigator ([name]).
- ii) The SAEs initial report should then be submitted to the UKM Ethics Committee in an expedited fashion.
- iii) SAEs should be reviewed and followed to resolution by the medical officers / PI / co-investigator in charge of study participant
- iv) A subsequent follow-up report will be submitted that documents any additional important information, including the resolution of SAEs.

3.10.8 AEs / SAEs follow-up at the end of study period

If AEs / SAEs occur or are still ongoing at the end of the study, the study participants will still be continuously followed up until the resolution of AEs / SAEs occur, except the PI deems that no further follow-up is necessary. The follow-up may take the form of 1) additional subject visits to the trial centre / hospital; 2) telephone calls to the subjects; 3) additional reporting in the form of letters from the treating physicians.

3.10.7 Study Halting Criteria

Participant enrolment and allocation and institution of interventions will be stopped if one of the following occur:

- a) Death related to microneedle or EMLA application
- b) Any participant experiences bronchospasm, laryngospasm or anaphylaxis within 24 hours post microneedle or EMLA application
- c) Any SAE related to microneedle or EMLA application
- d) Any AE of grade 3 and above or any SAE that cannot obviously be implicated on other causes
- e) Any study participant who develops abscess / ulceration / erosion at the site(s) of microneedle or EMLA application

3.11 Quality Control

To ensure the quality of data collection, the following procedures will be followed: 1) all parties involved in this study (including outcome assessors) will be required to attend a training session to standardize procedures and data collection; 2) the CRFs will be continuously checked for data accuracy and consistency, missing data and other data collection-related issues on fortnightly basis; 3) the biostatistician ([name]) will be notified on missing data or any data inaccuracy and tasked with formulating remedial measures; 4) the principal investigators and the biostatistician will conduct a final review of the detailed reports on screening, enrolment, follow-up and any data completeness / accuracy; 5) upon the clearance obtained from the principal investigators and biostatistician, the data from each CRF will be eventually entered into the SPSS spreadsheet.

3.12 Sample size calculation

The determination of sample size is carried out using G*Power software, version 3.1.9.6 (Universitat Kiel, Germany; February 2020) using the F-test family, Repeated Measure (RM) ANOVA within and within-between interaction sub-options. The type I error (α) and the study power ($1 - \beta$, where β = type II error) are fixed at 0.05 and 0.80, respectively.

Due to scarcity of information from previous literature on paediatric population, we could not use the parameter estimates (standard deviation of the differences, mean differences between pairs) from prior studies as guides for our sample size calculation. However, to circumvent this, we utilise Cohen's guideline on choosing the effect size for this study.⁴⁴ We assumed that the Cohen's d is large ($d = 0.8$) and used this as our effect size. It had been demonstrated by a

previous study on the efficacy of microneedle as a delivery method for 5% lidocaine dental gel (Septodont, UK) that the effect size could be that large, thus justifying our choice of effect size in general.⁴⁵ For objectives 1 and 2, we used the RM-ANOVA within-group comparison sub-option and fix the number of groups and measurements to 1 and 4, respectively. Based on prior guidelines, moderate-to-high correlations between the within-group measurements ($r = 0.7$) are assumed.^{46,47} For non-sphericity correction (ϵ), a value of 0.75 is assumed since the sphericity assumption is rarely fulfilled in practical and actual trial setting due to unequal correlations between measurement pairs and the chosen ϵ value is midway between its lower bound of 0.5 and maximal value of 1 to fairly preserve the RM-ANOVA test against inflated type I error rate (α) when non-sphericity occurs.⁴⁸⁻⁵¹ Hence, for objectives 1 and 2, we require a sample size of 23 subjects. Assuming a 10% attrition (drop-out) rate, the total sample size is 26 ($n_{\text{total}} = 26$).

For objective 2, we could not calculate the sample size since we don't have the estimate of the standard deviation of the differences (denoted by (s) henceforth) between the two methods for pain evaluation (the VAS score and the skin conductance algesimeter index obtained via PainMonitor™). Information on (s) is required since the sample size formula for evaluating limit of agreement require s parameters to be explicitly specified. However, we could roughly assess the precision of the limit of agreements (as per (s) magnitude) based on the sample size proposed for objective 1 and 2 using the formula recommended by the original authors.⁵² Based on Bland and Altman (1986), the 95% CI of limit of agreement is given by:

$$\pm 1.96 * \sqrt{3/n} * s^{52},$$

where s = standard deviation of the differences between VAS score and the skin conductance algesimeter index. If we assume a sample size of 24, then the precision of the limit of agreement is:

$$\pm 1.96 * \sqrt{3/26} * s = \pm 0.67 * s,$$

which we deem a satisfactory precision in our case.

However, due to absence of an estimate of (s) from prior studies, the actual precision could not be accurately estimated, thus highlighting the importance of (s) in the actual sample size calculation. Thus, it is hoped the estimate of (s) obtained from this study will be used as a guide for calculating a sample size for a future follow-up study that can answer this study objective more reliably. However,

Hence, the biggest overall sample size required for this study is 26 ($n_{\text{total}} = 26$).

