3.14 Planned Statistical Analysis

The data will be initially checked and cross-examined with the information in the data collection sheet for accuracy, consistency and the amount of missing data. Missing data will be treated as Missing At Random (MAR) and multiple imputation will be considered to impute the missing values in order to reduce the biasness of the parameter estimates. Any variable with serious missing data problem (more than 40%) will be dropped from further analysis.^{54,55} All patients will be analysed according to the original randomization group, based on the intention-to-treat (ITT) analysis.

All data will be descriptively summarized as mean and standard deviation (SD) for the normally-distributed numerical variables (or median and interquartile range (IQR) for the non-normally distributed numerical variables) and frequency and percentage for categorical variable. For numerical data, the normality assumptions will be evaluated subjectively using the histogram with overlying normal distribution curve, box and whisker plot and steam-and-leaf diagrams and objectively using the Kolmogorov-Smirnov and Shapiro-Wilks tests ($p>0.05$ indicates normal distribution assumption is met). Fisher's coefficient of skewness will be subsequently utilized to assess the severity of skewness in non-normally distributed numerical variables using the following formula:

Fisher's coefficient of skewness: Skewness / standard error of skewness

Any value outside ± 2 range will indicate extreme skewness.⁵⁶

For the first and second objectives, repeated measure ANOVA and generalized mixed effect model (GLMM) with an identity link function will be used to assess and estimate the differences in terms of VAS score means between the periods of interventions, considering intra-subject correlations. For repeated measure ANOVA, Mauchly's test of sphericity will be used to assess the sphericity assumption. If sphericity assumption is violated, the Greenhouse-Geisser correction will be used if $\varepsilon < 0.75$ or the Huynh-Feldt correction if $\varepsilon > 0.75$.⁵⁷ Within-group analysis will be used to assess the significance of mean VAS score differences between treatment pairs. To assess the presence of carryover effect, the within group-between treatment sequence interaction effect will be assessed for statistical significance.

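### Section 3.12: the lower bound given for epsilon is wrong for four measurements, and the 23 subjects cannot be derived from the inputs stated

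*Combined protocol and SAP*

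**What the plan says.** Section 3.12 sizes objectives 1 and 2 (the VAS score and the skin conductance index compared across the four treatments) with the G*Power repeated-measures ANOVA procedure at alpha 0.05 and power 0.80.

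- **Effect size:** "We assumed that the Cohen's d is large ($d = 0.8$) and used this as our effect size". No Cohen's f, conversion from d to f, pattern of the four means or effect-size option is given.
- **Layout:** the authors use the within-group option and "fix the number of groups and measurements to 1 and 4, respectively".
- **Correlation:** "moderate-to-high correlations between the within-group measurements ($r = 0.7$) are assumed".
- **Epsilon:** 0.75 is assumed. The reason for this particular figure is that the chosen "value is midway between its lower bound of 0.5 and maximal value of 1".
- **Result:** "Hence, for objectives 1 and 2, we require a sample size of 23 subjects". With 10% attrition this becomes 26, which the section then carries forward as the overall sample size.

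For the analysis, section 3.14 plans Mauchly's test and adds: "If sphericity assumption is violated, the Greenhouse-Geisser correction will be used" when epsilon is below 0.75, with the Huynh-Feldt correction above it.

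**The concern.** The lower bound of epsilon depends only on the number of repeated measurements, and the protocol fixes that number at four. The bound quoted belongs to a design with three. It is the only argument offered for 0.75 as opposed to another value, and 0.75 feeds directly into the 23.

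The second difficulty is that a repeated-measures F test is powered on f, whereas the section supplies d. Going from one to the other requires the pattern of the four means, and a decision on whether 0.8 is scaled by the SD of the scores (raw d) or by the SD of the paired differences (d_z). At r = 0.7 these are different effects: d_z = 0.8 is 0.8 × √(2 × (1 − 0.7)) = 0.62 SD of the scores, while raw d = 0.8 is 0.80 SD. A reader therefore cannot tell which difference the trial has 80% power to detect, or whether the stated correlation was used at all.

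**Working it through.** **Inputs (section 3.12):** m = 4 measurements, one group, alpha 0.05, target power 0.80, r = 0.7, epsilon (eps) = 0.75, effect size 0.8, attrition 10%.

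**Formula (assumed to be the procedure's default form):** noncentral F with df1 = 3 × eps, df2 = 3 × eps × (N − 1) and λ = f² × N × 4 × eps / (1 − r).

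**1. Epsilon.** The lower bound is 1/(m − 1).
- Three measurements: 1/2 = 0.50.
- Four measurements: 1/3 = 0.33.
- Midpoint for four: (0.333 + 1)/2 = 0.667. The stated 0.75 is (0.5 + 1)/2, the midpoint for three.

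**2. Smallest N for 80% power with all the stated inputs.**
- 0.8 entered as f: N = 4.
- Raw d = 0.8 as the range of the four means:
  - two means at the midpoint, f = 0.8/√8 = 0.283: N = 14
  - evenly spaced, f = 0.298: N = 13
  - one mean apart from three, f = 0.346: N = 10
  - two and two, f = 0.8/2 = 0.400: N = 8

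None is 23. At r = 0.7 this formula returns 23 only for f of about 0.215 to 0.220.

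**3. What does give 23.** Setting λ = 0.64 × N × eps gives, at N = 23, λ = 0.64 × 23 × 0.75 = 11.04 with df 2.25 and 49.5, and power 0.815. At N = 22 power is 0.795, so 23 is the minimum. The multiplier 0.64 can arise in at least four ways:
- 0.8 entered directly in a form without r, λ = f² × N × eps: 0.8² = 0.64
- f = 0.4 with r = 0: 0.16 × 4 = 0.64
- raw d = 0.8, two means at the midpoint, r = 0.5: 0.08 × 4/0.5 = 0.64
- d_z = 0.8, two means at the midpoint: f² = 0.16 × (1 − r), so 0.16 × (1 − r) × 4/(1 − r) = 0.64 whatever r is (at r = 0.7, f = 0.219)

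The first and fourth do not depend on r. The second and third contradict the stated r = 0.7.

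**4. Attrition.** 23/0.9 = 25.6, rounded up to 26. This step reproduces.

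**5. Effect on power.**
- Raw d = 0.8, r = 0.7, 23 completers: at least 96.4% at eps 0.75 and at least 94.8% at eps 0.67 (the lowest is the pattern with two means at the midpoint).
- λ = 0.64 × N × eps, 23 completers: 81.5% at eps 0.75 and 77.8% at eps 0.67.
- The same λ at eps 0.67 with 26 completers: 83.3%. The smallest N for 80% would be 25, or 28 after attrition (25/0.9 = 27.8).

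**The case against.** The best defence is that 23 is not a wrong number. It comes out exactly if 0.8 is entered as it stands in a form that does not use r, which matches the statement that d was used as the effect size and needs no assumed pattern of means. The section also refers to the "standard deviation of the differences, mean differences between pairs", which makes a paired d_z plausible. This stands: 23 is attainable and should not be called an arithmetical error. But whether the software option chosen works in that way cannot be settled from the documents, and if it does, the stated r = 0.7 had no role in the result. The text needs to say so.

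It can also be said that nothing obliges the sponsor to plan at the midpoint of the range. That is correct. 0.75 lies between 0.33 and 1 and may be kept; only the reason given for it fails.

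Three stronger readings are tempting, and the documents do not support them.
- **The trial is underpowered.** With raw d = 0.8 and the stated r, 23 completers are more than enough.
- **The wrong bound inflates type I error.** The planning value affects power only. The test itself is governed by the sphericity corrections in section 3.14.
- **The interaction option produced the 23.** The section opens by naming "Repeated Measure (RM) ANOVA within and within-between interaction sub-options", but then states that the within-group option was used for objectives 1 and 2.

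**Conclusion.** The lower bound of 0.5 is wrong on the protocol's own count of four measurements, and with it the argument for 0.75. This is certain and rests on no assumption about the software.

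The 23 does not follow from the inputs as written under the default within-subject formula, which gives 4 to 14. It does follow under several unstated choices, and the text does not say which was made. This rests on the noncentral-F formula shown and on the four patterns of means listed.

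The practical consequence is limited. Only if λ = 0.64 × N × eps was used and epsilon is taken as 0.67 does power at 23 completers fall below target, to 77.8%. On that reading 80% is kept with 23 completers as long as epsilon is at least 0.715, and with all 26 as long as it is at least 0.597. The point should be corrected because the section is the sole basis for the sample size, not because the trial has been shown to be too small.

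**What to change.** Keep 26 participants and rewrite the paragraph in section 3.12:

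1. Give the lower bound of epsilon for four measurements as 0.33.
2. Justify 0.75 on other grounds, or keep it and show 0.67 as a sensitivity value.
3. From the saved software run, state the effect size entered, the effect-size option, whether 0.8 is a raw d, a d_z or an f, and any pattern of means assumed. Say whether r = 0.7 was used; if it was not, correct or remove it.
4. Restate the power to match. If the run corresponds to λ = 0.64 × N × eps, that is 81.5% at epsilon 0.75 and 77.8% at 0.67 with 23 completers, and 83.3% at 0.67 with 26.

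The cost is one paragraph and a check of the run, with no extra patients and no change to the analysis. The downside is that the stated power may look slightly less favourable. If the run was not saved, it must be repeated and may not return 23.

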3.13 Operational definitions of study variables

a) Independent variables

i) **Age:** The age of a study participant at the first study visit. The variable will be measured in years and month and modelled as a continuous numerical variable and will not be categorised into separate age groups.

ii) **Gender:** A categorical variable that will be recorded in the SPSS data frame as 0 = female (base category) and 1 = male. Missing data shall be recorded as 999

iii) **Ethnicity:** A categorical variable that will be recorded in the SPSS data frame as 0 = Malay (base category); 1 = Chinese; 2 = Indian; and 3 = Other ethnicity. Missing data shall be recorded as 999.

iv) **Body mass index (BMI):** A continuous numerical variable that is calculated using the standard body mass index formula; $BMI = \text{kg} / \text{m}^2$. This variable will be categorised according to Kuczmarski et al. (2000) classification⁵³:

<5% percentile = underweight (SPSS code: -1)

5% - <85% percentile = normal BMI (SPSS code: 0; base category)

85% - 95% percentile = Overweight (SPSS code: +1)

>95% percentile = Obese (SPSS code: +2)

The categorized variable will then be used as a predictor variable for statistical modelling purposes. Missing data will be recorded as 999 in the SPSS spreadsheet.

iv) **Intervention groups:** A categorical variable representing the types of interventions received by the study participants in each study visit. This variable will be recorded in the SPSS data frame as 0 = 1-FTU-EMLA only group (control, base category); 1 = MN + 0.5FTU EMLA (30 minutes), 2 = MN + 1FTU EMLA (15 minutes), 3 = MN + 1FTU EMLA (30 minutes).

v) **Baseline VAS score:** A continuous numerical variable that will be measured before the administration of intervention. This will be used as a predictor variable to control the confounding effect of heterogenous baseline VAS scores among study participants. Missing data will be recorded as 999 in the SPSS spreadsheet.

vi) **Baseline pain score obtained via PainMonitor™ device:** A continuous numerical variable that will be measured before the administration of intervention. This will be used as a predictor variable to control the confounding effect of heterogenous baseline VAS scores among study participants. Missing data will be recorded as 999 in the SPSS spreadsheet.

b) Dependent (outcome variables)

i) **VAS score (15- and 30-minutes post EMLA application during IV cannulation):** A continuous numerical variable that will be measured during each visit; 15 minutes after EMLA application and 30 minutes after EMLA application. Missing data will be recorded as 999 in the SPSS spreadsheet.

ii) **Pain score from PainMonitor™ device (15- and 30-minutes post EMLA application):** A continuous numerical variable that will be measured during each visit: 15 minutes after EMLA application and 30 minutes after EMLA application. Missing data will be recorded as 999 in the SPPS spreadsheet.

3.14 Planned Statistical Analysis

The data will be initially checked and cross-examined with the information in the data collection sheet for accuracy, consistency and the amount of missing data. Missing data will be treated as Missing At Random (MAR) and multiple imputation will be considered to impute the missing values in order to reduce the biasness of the parameter estimates. Any variable with serious missing data problem (more than 40%) will be dropped from further analysis.^{54,55} All patients will be analysed according to the original randomization group, based on the intention-to-treat (ITT) analysis.

All data will be descriptively summarized as mean and standard deviation (SD) for the normally-distributed numerical variables (or median and interquartile range (IQR) for the non-normally distributed numerical variables) and frequency and percentage for categorical variable. For numerical data, the normality assumptions will be evaluated subjectively using the histogram with overlying normal distribution curve, box and whisker plot and steam-and-leaf diagrams and objectively using the Kolmogorov-Smirnov and Shapiro-Wilks tests ($p>0.05$ indicates normal distribution assumption is met). Fisher's coefficient of skewness will be subsequently utilized to assess the severity of skewness in non-normally distributed numerical variables using the following formula:

Fisher's coefficient of skewness: Skewness / standard error of skewness

Any value outside ± 2 range will indicate extreme skewness.⁵⁶

For the first and second objectives, repeated measure ANOVA and generalized mixed effect model (GLMM) with an identity link function will be used to assess and estimate the differences in terms of VAS score means between the periods of interventions, considering intra-subject correlations. For repeated measure ANOVA, Mauchly's test of sphericity will be used to assess the sphericity assumption. If sphericity assumption is violated, the Greenhouse-Geisser correction will be used if $\varepsilon < 0.75$ or the Huynh-Feldt correction if $\varepsilon > 0.75$.⁵⁷ Within-group analysis will be used to assess the significance of mean VAS score differences between treatment pairs. To assess the presence of carryover effect, the within group-between treatment sequence interaction effect will be assessed for statistical significance.

For GLMM, the Restricted Maximum Likelihood (REML) estimator will be used to estimate the model parameters. The unadjusted and adjusted estimates of the parameters obtained using the GLMM will be examined, with and without the consideration of periodic effects. Random intercept model and robust variance estimators will be used for the calculation of standard errors. Likelihood ratio test will be utilized to compare the nested models and Akaike Information Criteria (AIC) and Bayesian Information Criteria will be used for comparing non-nested models. Multicollinearity between fixed effects (age, sex and treatment effects) will be evaluated using bivariate correlations. Besides, interaction effects (effect modification) between significant fixed predictors will also be assessed by evaluating the significance of interaction terms. Residual diagnostics will also be performed to ensure the validity of model assumptions and the presence of outliers and influential points will be investigated to ensure that they do not influence the model parameter estimates. The presence of any influential point will then be removed or corrected if these are due to measurement errors or wrong data entry or retained if the values are authentic. We will also carry out sensitivity analyses to investigate the effects of missing data under the Missing At Random (MAR) framework.

For the third and fourth objectives, the correlation between VAS pain score and PainMonitor™ device is tested using Pearson correlation coefficient if both VAS pain scores and PainMonitor™ device are normally distributed (Gaussian) and Spearman coefficient will be used if at least one pain scores (obtained by either measuring modality) are not normally distributed. Intraclass correlation coefficient (ICC) will be computed to assess the agreement between the VAS scores obtained using the two different modalities (VAS pain score vs PainMonitor™ device) and the results will be interpreted according to the Koo-Li criteria.⁵⁸ The Bland and Altman (B&A) plot will be obtained to further assess the agreement between the two scores. The limits of agreement obtained will be assessed to ensure there is an acceptable agreement between the pain measurement modalities.

For each analysis, the significant threshold for p value is fixed at 0.05 and 95% confidence interval (CI) will be obtained for each parameter estimates. Data analysis will be performed using Statistical Package for Social Science (SPSS™) (IBM Corp. Released 2020. IBM Statistics for Windows, Version 27.0, Armonk, NY: IB Corp) and STATA™ version 15 (StatCorp. 2017. Stata Statistical Software: Release 15. College Station, Texas: StataCorp LP).

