3.1 Research Design

This is a prospective, phase II, single-centre, single-blind, cross-over, randomized negative-controlled (without microneedle (MN)) trial at Hospital Canselor Tuanku Muhriz (HCTM), Universiti Kebangsaan Malaysia. Eligible participants will be randomized in a cross-over fashion to one of 24 treatment sequences as shown in **Figure 4**.

This crossover design is chosen over the more conventional parallel-group randomized trial since the lesser intra-patient variability than the inter-patient variability, thus minimising the required sample size. The study investigators also do not anticipate the inherent disadvantages associated with this trial design (greater attrition rate, prolonged carry-over effects and the inconsistency of participant's condition) will be present in this study.

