3.8 Randomization procedure

For random allocation, simple randomization with random allocation rule (RAR) will be used by which a list of random numbers will be generated in a balanced 1:1 ratio (based on 24 different treatment sequences) using the randomizeR package version 20.0 executed on R platform.³⁴ The list of generated random numbers will be used to allocate the study participants to either intervention or control branch. The allocation sequence generated will be kept in a password-protected document that is only accessible to the statistician to maintain allocation concealment. To further guarantee allocation concealment is satisfactory, randomisation code will not be revealed until the participants have been definitively recruited into the trial, which is after all baseline measurements are made and all eligibility criteria are deemed fulfilled. Besides, allocation concealment is further assured by ensuring the information on the intervention allocation is only given to the person who will be administering the allocation via secured phone calls (central randomization). Consecutive recruitments will be made until the final intended sample size is reached.

For this study, the study participants, outcome assessors, care providers and data handlers will be blinded to the study interventions. Only the statistician and the person who will be administering the interventions will be unblinded to the study interventions. Besides, unique code to indicate each treatment sequence assignment will be utilised to ensure that the unintentional / intentional unblinding of one trial participant will not compromise the integrity of blinding for the rest of study participants. The main unblinded trial persons (the statistician and the key person who will be administering the intervention) are instructed not to divulge the identity of the allotted treatments to other blinded trial persons. The success of blinding will be determined by asking the blinded trial persons (e.g. study participants, care providers, outcome assessors) to guess the interventions received and then compare the results obtained with what would be anticipated by chance. Blinding indices such as James' Blinding Index or Bang's blinding Index could also be computed to objectively evaluate the success of blinding.^{35,36}

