3.9.2 Administration of interventions / controls

Prior to the administration of intervention / control, relevant clinic-demographic profiles (age, gender, ethnicity, anthropometric measurements, presence of comorbidities, thalassemia types etc) will be recorded and entered in the case report forms (CRFs) that are specifically designed for this study. This research study uses EMLA Cream (lidocaine 2.5% and prilocaine 2.5%) as the topical anaesthetic agent. EMLA Cream is a eutectic emulsion mixture of lidocaine and prilocaine at 1:1 ratio (i.e. each gram of EMLA cream contains lidocaine and prilocaine, 25 mg each). A eutectic mixture has a lower melting temperature than each constituent's melting temperature. The anaesthetic efficacy of EMLA cream will be assessed via pain induced by intravenous cannulation and the primary endpoint is the participant's VAS score measured after applying EMLA Cream (with and without MN application) for 15 and 30 minutes.

The window period given to EMLA Cream for its effect to work will be based on the usual clinical practice observation where it is usually applied for 30 minutes prior to intravenous catheterization. The rationale behind it is due to logistical issues and for the day care's operational convenience. Nevertheless, in a busy clinical setting, the application time is sometimes shortened to 15 minutes for slight anaesthetic effect. Thus, the study investigators postulate that, with the aid of microneedle, the time to onset of action for EMLA Cream could be greatly reduced, thus requiring less time to achieve its maximal effects.

According to the routine hospital protocol, all study participants received their blood transfusion based on the Good Clinical Practice (GCP) guidelines. For each participant, the individual will be randomized to one of the 24 treatment sequences (**Figure 4** and **Table 1**) and there will be a minimum of 3-weeks washout period before administering the next intervention. **Figure 5** illustrated the complete clinical flow for the first and subsequent visits, which includes the preliminary recruitment and randomization phases.

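### The plan's only carryover test, a treatment-by-sequence interaction over 24 sequences, is close to uninformative with 26 participants and absorbs period effects

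*Combined protocol and SAP*

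**What the plan says.** Section 3.1 states: "Eligible participants will be randomized in a cross-over fashion to one of 24 treatment sequences". Table 1 lists all 24 orders of the four interventions. Section 3.8 says "simple randomization with random allocation rule (RAR) will be used", and the same sentence asks for equal allocation over the 24 sequences. Section 3.9.2 says "there will be a minimum of 3-weeks washout period before administering the next intervention". Section 3.12 concludes: "Assuming a 10% attrition (drop-out) rate, the total sample size is 26". That calculation uses one group and four measurements, so sequence plays no part in it.

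Section 3.14 applies repeated-measures ANOVA and a mixed model to objectives 1 and 2. Under the ANOVA it says: "To assess the presence of carryover effect, the within group-between treatment sequence interaction effect will be assessed for statistical significance". No period term is named for the ANOVA. The mixed model is to be examined "with and without the consideration of periodic effects", and no preceding-treatment term is named for it. Nothing says what follows from a significant or a non-significant carryover result.

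**The concern.** A 24-level sequence factor uses almost all the information in 26 participants. The carryover signal is spread over 69 interaction df, and very little is left to estimate error. The interaction is also not specific to carryover. Within a sequence each treatment always falls at the same visit, so a drift in pain scores over visits appears as treatment differing by sequence.

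At stake is what the report can say. A crossover trial is expected to comment on carryover, and this is the only check planned. A non-significant result would be nearly certain whether or not carryover exists, and a significant one could simply be a visit trend. The 24-sequence design itself does support a proper carryover estimate; the term is missing from the analysis.

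**Working it through.** **Inputs.** 24 sequences (3.1, Table 1); four visits; 23 participants required and 26 with 10% attrition (3.12), where 23/0.9 = 25.6, rounded up to 26; significance threshold 0.05 (3.14). The plan gives no power or sample size for the carryover test, so there is no such figure to reproduce.

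**Assumptions.** The documents give no size for carryover or drift. I take equal carryover after each microneedle arm and none after control, in units of the residual (within-participant) SD, with independent errors. For scale, if d = 0.8 is in total-SD units and r = 0.7, as in 3.12, it equals 0.8/√(1 − 0.7) = 1.46 residual SD.

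**Degrees of freedom, near-balanced allocation.**
- Numerator: (24 − 1) × (4 − 1) = 69.
- Error: 3 × (N − occupied sequences).
- N = 26 with all 24 occupied: 3 × 2 = 6; critical F(69,6) = 3.73.
- N = 25: 3 × 1 = 3; critical F(69,3) = 8.57.
- N = 24, one per sequence: 0, so the test cannot be computed.

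Now lose 3 of 26, starting from 22 sequences with one participant and 2 with two. Of the 2,600 possible losses, 1,540 (59.2%) leave 6 error df, 968 (37.2%) leave 3 and 92 (3.5%) leave none. The test usually runs, but on very few error df.

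**Power at N = 26, near-balanced.** Power comes from the noncentral F, with noncentrality equal to the sum of squares between nested designs. The planned test compares participant + treatment with participant + sequence × treatment. The alternative adds preceding treatment (3 df) to participant + treatment + period.

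| Carryover (residual SD) | Planned test, F(69,6) | Preceding-treatment test, F(3,69) |
|---|---|---|
| 0.5 | 0.06 | 0.26 |
| 1.0 | 0.10 | 0.82 |
| 2.0 | 0.29 | >0.99 |

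The second decimal depends slightly on which two sequences are doubled.

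**Mixing with period.** The design matrix for participant + sequence × treatment has rank 98. Adding period columns leaves it at 98, so all period effects lie inside the 69-df interaction. With no carryover and a linear trend over visits, the planned test rejects as follows.

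| Trend per visit (residual SD) | Rejection, planned test |
|---|---|
| 0.1 | 5.2% |
| 0.25 | 6.5% |
| 0.5 | 12% |
| 1.0 | 41% |

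The preceding-treatment test, adjusted for period, stays at 5% throughout.

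**If simple randomisation is taken literally.** Expected occupied sequences are 24 × (1 − (23/24)^26) = 16.1, giving about 45 numerator and 30 error df. Averaged over simulated allocations, the planned test has power of about 0.32 at 1 SD and 0.95 at 2 SD. With no carryover, the 0.5 SD trend gives about 46% rejection. The preceding-treatment test has power of about 0.78 at 1 SD.

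**With 23 completers.** The preceding-treatment test has 60 residual df and power of about 0.76 at 1 SD.

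**The case against.** The strongest reply is that little depends on this test. A washout of at least three weeks against half-lives of 1.6 hours (section 1.4) makes drug carryover implausible. Section 3.1 does not anticipate prolonged carryover. No decision rule is attached, and a full 24-sequence design with equal filling is balanced for period and preceding treatment. All of this stands. It limits the severity, and no bias in the treatment contrasts has been shown. It does not make the test's result reportable.

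Second, the false-positive figures depend on the assumed drift. A trend of 0.5 SD per visit is 1.5 residual SD from first to last visit, about the size of the planned effect (1.46). Under near-balanced allocation smaller drifts leave rejection near 5%. That is fair. The inflation is a matter of degree, but the mixing itself is structural.

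Third, under literal simple randomisation the test would detect a 2 SD carryover well. That is true, but the same extra error df make it react far more strongly to a visit trend.

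Fourth, the wording leaves open whether the within-participant factor is treatment or visit. The sentence just before it applies within-group analysis to treatment pairs, which supports the treatment reading used here. On the visit reading, period would be a main effect, but the interaction would then contain the direct treatment effects, which is no better.

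Fifth, the mixed model already considers period. It does so optionally and separately, without a carryover term, and so does not repair the ANOVA test.

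**Conclusion.** The concern holds and should be fixed. Under near-balanced allocation the planned test has at most 6 error df and power of at most 0.29 for carryover up to 2 residual SD. Under either allocation reading it cannot separate carryover from a period effect. The df and rank results follow from the design, on the reading that the within-participant factor is treatment. The power and rejection figures rest on the assumed carryover pattern, linear drift and independent errors. The finding does not show that carryover exists. It shows that the planned check could not support a statement about it either way.

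**What to change.** In section 3.14, delete the sequence-interaction test. Pre-specify the mixed model with treatment and period as fixed effects and participant as random effect. As a sensitivity analysis, add the treatment given at the preceding visit (3 df; none at visit 1). Report the carryover estimates and the treatment contrasts with 95% confidence intervals, and state that the result will not be used to choose the primary model. Keep the 24 sequences.

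This changes SAP wording only; allocation, visits and sample size stay as they are. With one participant per sequence, the variance of a treatment contrast in the sensitivity analysis rises from 0.0833σ² to 0.0917σ², a ratio of 1.10. Over simulated patterns of 23 completers the rise is 7% to 17%. The primary analysis does not bear this cost. The replacement has limits too: power for a 0.5 SD carryover is only about 0.26, and the 95% confidence interval for a carryover contrast against control has a half-width of about 0.70 residual SD at N = 26. The interval should therefore be reported, not only a p-value.
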